**Exploratory CV Safety Analyses**

- infarction (NSTEMI), ECG not interpretable, ECG not available], and Q wave classification (Q wave MI, Non Q wave MI, ECG not interpretable, ECG not available).
- Summaries of adjudication details of stroke will include the number and percentage of events by outcome of stroke (fatal or non-fatal), type of stroke (ischemic, hemorrhagic, or undetermined) and ischemic details (with/without hemorrhagic transformation) and location if hemorrhagic (intraparenchymal, intraventricular, subarachnoid, retinal, unknown location).
  - Summaries of adjudication details of heart failure will include the number of events by type: hospitalization for heart failure, heart failure requiring urgent ER/ED visit, heart failure requiring urgent office/practice visit, and fatal heart failure events identified by cause of death only.
  - Summaries of adjudication details of thromboembolic events will include the number and percentage of events by type of thromboembolic event (DVT, PE, VAT).
    - Summaries of PEs will include outcome of PE (fatal or non-fatal).
    - Summaries of VATs will include type of VAT (AV fistula, AV graft, central venous catheter, other), method of diagnosis (ultrasound/Doppler, AV imaging, CVC imaging, other), and treatment (thrombolytic therapy, thrombectomy, angioplasty, stent, surgical intervention, not specified).
  - A summary of adjudicated supportive CV endpoints above (except all-cause hospitalization) will be provided to include the number and percentage of subjects and the number of events for each endpoint.
  - The model results presentation for the endpoints above plus MACE or Thromboembolic Events or Hospitalization for CHF will be provided to include within-group incidence rates per 100 person-years (along with two-sided 95% CI) and difference in rates between treatments (along with two-sided 95% CI). For composite endpoints, the number and percentage of the type of first occurrence will be provided by treatment group.
  - A summary of all-cause hospitalization will be provided by treatment group including summaries of the number of hospitalizations per subject, average length of stay per hospitalization, and primary diagnosis at discharge by system organ class and lower level term.
  - Time from Randomization to first occurrence of adjudicated MACE event or end of trial will be evaluated using Kaplan-Meier (KM) methodology and displayed graphically for the comparison of daprodustat vs. rhEPO.
  - Summary of concordance between events referred for adjudication and adjudicated endpoint events (Positively Adjudicated or Negatively Adjudicated) will be presented.
  - A listing of all MACE events occurring during the study will be provided and will include treatment, site ID, unique subject ID, Subject ID, select demographic information, event type, event date, and study day.
  - A listing of all all-cause mortality events that occur during the study will be provided. This listing will include treatment, site ID, unique subject ID, select demographic information, event date, study day, and cause of death.

 Adjudicated events used where available.

CONFIDENTIAL

204837

*Relationships between daprodustat  $C_{max}$ /dosing and MACE/Combined MACE-related endpoint*

Endpoint / Variables	
Daprodustat Safety Dose Parameters	
Dose at first MACE	The TIW daprodustat dose at the time of the subject's first on-treatment adjudicated MACE. If the subject does not have an on-treatment adjudicated MACE, this value is missing.
Final Dose for Subjects without MACE	For subjects without an on-treatment adjudicated MACE, this is the subject's final TIW daprodustat dose during the study.
Dose at first MACE++	The TIW daprodustat dose at the time of the subject's first on-treatment adjudicated MACE + thromboembolic event + hospitalization for CHF. If the subject does not have an on-treatment adjudicated MACE + thromboembolic event + hospitalization for CHF, this value is missing.
Final Dose for Subjects without MACE++	For subjects without an on-treatment adjudicated MACE + thromboembolic event + hospitalization for CHF, this is the subject's final TIW dose during the study.
Daprodustat Safety Special Parameters	
C max /Dose at first MACE	C max extrapolated to dose at MACE: C max /1mg multiplied by the TIW daprodustat dose at the time of the subject's first on-treatment adjudicated MACE.
C max /Final Dose for subjects without MACE	For subjects without an on-treatment adjudicated MACE, this is the subject's C max /1mg multiplied by the subject's final TIW daprodustat dose during the study.
C max /Dose at first MACE++	C max extrapolated to dose at MACE + thromboembolic event + hospitalization for CHF: C max /1mg multiplied by the TIW daprodustat dose at the time of the subject's first on-treatment adjudicated MACE + thromboembolic event + hospitalization for CHF.
C max /Final Dose for subjects without MACE++	For subjects without an on-treatment adjudicated MACE + thromboembolic event + hospitalization for CHF, this is the subject's C max /1mg multiplied by the subject's final TIW daprodustat dose during the study.
Planned Exploratory Displays	

 
Boxplot of Cmax/Dose at on-treatment MACE by subjects with or without on-treatment MACE
 
	

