10.3.3.3. Other Exploratory Analyses

The exploratory graphics described below will be created.

- Scatter plots of mean weekly daprodustat dose over the EP vs. the percent time within the Hgb target range during the EP
- Scatter plots of mean weekly three-times weekly daprodustat dose over 52 weeks vs. mean Hgb over the 52-week treatment period
- Boxplots of mean weekly three-times weekly daprodustat dose, while on study treatment for participants without MACE, and before the event for participants with MACE or combined safety endpoint
- Boxplots of Cmax of three-times weekly dosed daprodustat extrapolated to daprodustat dose at PK sample multiplied by the daprodustat dose at the time of MACE or combined safety endpoint (or end of study if no endpoint) by participants with or without MACE or combined safety endpoint

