**CONFIDENTIAL**

204837

- Boxplot of Cmax/Dose at on-treatment MACE + thromboembolic event + hospitalization for CHF by subjects with or without on-treatment MACE + thromboembolic event + hospitalization for CHF
- Boxplot of Average TIW Dose at on-treatment MACE by subjects with or without on-treatment MACE
- Boxplot of Average TIW Dose at on-treatment MACE + thromboembolic event + hospitalization for CHF by subjects with or without on-treatment MACE + thromboembolic event + hospitalization for CHF
- Average TIW daprodustat dose will be summarized using mean, standard deviation, minimum, P25, median, P75, and maximum by participants with and without MACE.
- Average TIW daprodustat dose will be summarized using mean, standard deviation, minimum, P25, median, P75, and maximum by participants with and without MACE + thromboembolic event + hospitalization for CHF.

Average TIW daprodustat dose = average TIW daprodustat dose while on study treatment for participants without MACE/Combined MACE-related endpoint and before the event for participants with MACE/Combined MACE-related endpoint.

For the figures and summaries described above, the “On-Treatment” time window (“last non-zero dose date +28 days”, see Section 14.4.1) will be used to decide whether a subject should be considered with MACE/Combined MACE.

Daprodustat Safety Dose parameters (Dose at first MACE, Final Dose for Subjects without MACE, Dose at first MACE++, Final Dose for Subjects without MACE++) will be summarized using mean, standard deviation, minimum, P25, median, P75, and maximum by participants with and without MACE and MACE ++. Daprodustat Safety Special parameters (Cmax/ Dose at first MACE, Cmax/ Final Dose for subjects without MACE, Cmax/ Dose at first MACE++, Cmax/ Final Dose for subjects without MACE++) will be summarized using mean, standard deviation, minimum, median, maximum geometric mean, standard deviation of log-transformed data, and %CVb. A listing of the Safety Dose Parameters and a listing of the Safety Special Parameters will be provided.

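### The dose–MACE and Cmax–MACE displays are not aligned on study time, so a trend in mean dose over the year could show up as an exposure–MACE difference that is not there

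*SAP*

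**What the plan says.** SAP 8.2 defines two kinds of contrast, each for MACE and for the wider composite that adds thromboembolic events and hospitalization for heart failure (MACE++).

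- **Point-in-time contrast.** A case contributes "The TIW daprodustat dose at the time of the subject's first on-treatment adjudicated MACE". A participant without an event contributes the "final TIW daprodustat dose during the study". Cmax per 1 mg is multiplied by the same two doses. These values feed the Cmax boxplots (Figures 3.007 and 3.008) and the Safety Special and Safety Dose Parameter tables (Tables 3.040 and 3.041).
- **Average contrast.** The dose boxplots (Figures 3.009 and 3.010, the first being "Boxplot of Average TIW Dose at on-treatment MACE by subjects with or without on-treatment MACE") and Tables 3.042 and 3.043 use a different quantity: "average TIW daprodustat dose while on study treatment for participants without MACE/Combined MACE-related endpoint and before the event for participants with MACE/Combined MACE-related endpoint".

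Protocol 10.3.3.3 plans the same Cmax contrast, with Cmax "multiplied by the daprodustat dose at the time of MACE or combined safety endpoint (or end of study if no endpoint").

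All eight displays use the PK population. Protocol section 4 lists the objective as exploratory and graphical, without testing. No section aligns the two groups on study time or warns the reader that they differ in it.

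**The concern.** Dose is titrated at visits every 2 to 4 weeks, so its distribution can change with time on study. An early event is recorded near the starting dose. A final dose is recorded after titration, typically near Week 52. The average contrast has a related fault: a case's average covers only the part of the year before the event, and a non-case's covers all time on treatment.

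These are the displays that serve the stated objective of relating daprodustat exposure to MACE. A reader who sees cases at lower or higher doses cannot tell from the display whether that reflects exposure or calendar position.

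**Working it through.** The documents give no figure for this comparison, so there is nothing to reproduce. The check asks how large the gap would be if MACE did not depend on dose at all.

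**Inputs from the documents.** Starting doses are 8, 12, 16 and 24 mg (protocol 5.5). The dose ladder is 2, 4, 8, 12, 16, 20, 24, 32 and 48 mg, with placebo below it (protocol 7.1 and 7.2.1.2). Visits are two-weekly to Week 8, then four-weekly. The daprodustat arm has 268 of 402 participants. Fewer than 80 MACE are expected (protocol 10.3.2), which is 80/402 = 19.9%, or at most about 80 × 268/402 = 53 in this arm at equal rates. The PK population needs an analysed post-baseline sample (SAP 4), taken at Week 8 or later (protocol 9.5).

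**Assumed, because the documents do not say.** Starting-dose mix 15/50/20/15%, mean 0.15×8 + 0.50×12 + 0.20×16 + 0.15×24 = 14.0 mg; step probabilities; a constant MACE hazard independent of dose, giving 20% or 10% over the year.

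**Closed form.** Let mean dose drift linearly to week T and then stay flat, with events uniform over 52 weeks. As a share of net drift:

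- Event dose versus final dose, all events: T/104. For T = 12, 28 and 52 this is 12%, 27% and 50%.
- The same for events from Week 8: (T − 8)²/(2T × 44), giving 1.5%, 16% and 42%.
- Pre-event average versus full average, all events: 23%, 30% and 25%; from Week 8: 14%, 24% and 21%.

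Averaging therefore does not remove the problem.

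**Simulation.** 600 trials of 268 participants per scenario, 20% MACE. The floor was 2 mg rather than placebo, and dropout was not modelled. Steps are up/down % per visit before Week 28, then from Week 28. Gaps are cases minus reference, in mg, shown as all events / events from Week 8.

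| Scenario | Mean dose, start to final | Event vs final dose | Pre-event vs full average | Event vs same-week event-free |
|---|---|---|---|---|
| No titration | 14.0 to 14.0 | 0.00 / -0.05 | 0.00 / -0.05 | 0.00 / -0.04 |
| Balanced: 20/20, 10/10 | 14.0 to 15.3 | -0.44 / -0.33 | -0.34 / -0.27 | +0.05 / +0.02 |
| Moderate up: 25/15, 10/10 | 14.0 to 18.7 | -1.19 / -0.71 | -1.41 / -1.02 | 0.00 / -0.03 |
| Strong up: 30/15, 15/10 | 14.0 to 22.1 | -2.77 / -1.89 | -2.33 / -1.74 | -0.04 / -0.01 |
| Down: 15/30, 10/15 | 14.0 to 10.1 | +0.92 / +0.61 | +1.04 / +0.82 | -0.09 / 0.00 |

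The closed form agrees. For moderate upward titration with T = 28, net drift is 18.7 − 14.0 = 4.7 mg, and 0.269 × 4.7 = 1.3 mg against 1.19 mg simulated. Balanced steps still raise the mean because the ladder is unequal (24 to 32 to 48 mg at the top) and has a floor. With 10% MACE and events from Week 8, the event-versus-final gaps for the four titration scenarios are -0.37, -0.57, -1.93 and +0.59 mg, and the same-week gaps stay within -0.05 to +0.06 mg.

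Scaled Cmax is Cmax per mg times dose, so the ratio carries over. Under strong upward titration the mean doses are 19.32 and 22.09 mg, so mean Cmax in cases would sit at about 19.32/22.09 = 87% of the reference if Cmax per mg is unrelated to dose.

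**Sensitivity.** A second simulation used other assumptions (mix 15/50/25/10%, 12 MACE per 100 person-years, 24% of participants moving one step every 4 weeks all year). Event versus final means were 14.3 v 15.1 mg (balanced), 15.3 v 17.3 and 16.1 v 19.7 mg (upward), and 12.2 v 10.9 mg (downward); the same-visit gap was at most 0.2 mg. Its constant step rate fits poorly with protocol 5.5, which expects adjustment mainly in the early months, and it takes all events, so I give it less weight.

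**The case against.** The strongest case against acting has four parts.

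1. **No drift is stated.** Protocol 5.5 chose starting doses intended to reach target without adjustment. With balanced titration the gap is only about 0.3 to 0.8 mg, on a ladder whose steps from 4 to 24 mg are 4 mg. This stands. A reader might infer that ordinary titration by itself creates a dose–MACE association. A material artefact needs a net trend in mean dose, and the documents neither predict one nor rule one out.
2. **The PK population trims early events.** A death before the sample at Week 8 or later cannot enter, although a non-fatal early case sampled later does. This stands, and shrinks the gap without removing it.
3. **Dose by visit is already displayed.** SAP 7.4.1 plans tables and plots of assigned and most recent dose by visit, and listings give study day of MACE and dose at event. A reader could suspect drift from these. But they leave the MACE comparison uncorrected, and the dose-by-visit displays use the randomized rather than the PK population.
4. **Nothing is tested.** Had a nominal 5% rank test been run on event versus final dose, it would have rejected in 2 to 4% of balanced and 4 to 6% of moderate upward simulations, about the nominal rate. Under strong upward or downward drift it reached up to 30% and 22%. This limits the importance of the point but does not make the contrast valid.

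A reader might also infer that post-hoc exposure–safety modelling hangs on these plots. The documents do not support that. The modelling sentence is in protocol 10.3.3.2, refers to the hemoglobin scatter plots listed there together with the study results, and says only that modelling may follow. The MACE boxplots are in 10.3.3.3, which has no such sentence.

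**Conclusion.** The misalignment is real and plain in the text, for both the point-in-time and the average contrast. Given a net dose trend, the displays can show an exposure–MACE difference with no true association, in a direction set by the trend. Under the main assumed scenarios the event-versus-final gap is about -0.4 mg with balanced titration and -2.8 to +0.9 mg overall, or -1.9 to +0.6 mg for events from Week 8. The average-dose displays shift by -2.3 to +1.0 mg with all events. A same-week reference brings the gap to about 0.1 mg or less. Every mg figure rests on the assumed starting-dose mix, step rates and MACE risk.

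It would be wrong to read this as all displays using the final dose (the dose boxplots and average-dose tables do not), or as a threat to a trial conclusion. No test, error rate or primary result is affected. This is a worthwhile refinement to exploratory output.

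**What to change.** In SAP 8.2, for Figures 3.007 to 3.010 and Tables 3.040 to 3.043:

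- For each MACE or MACE++ case, add the dose, the average dose to date, and Cmax scaled to that dose, of PK-population participants who are on treatment and still event-free on the same study day. Participants whose event comes later belong in this reference until it occurs. Alternatively, plot the case value minus the median of that reference set.
- Footnote the existing contrasts as not aligned on study time, with a pointer to the dose-by-visit displays.
- Record the addition in SAP Table 1 as a change from protocol 10.3.3.3, whose reference value is the dose at event "or end of study if no endpoint".

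The cost is modest reprogramming of four figures and four tables and a display that takes slightly longer to explain. Dose by visit is already derived, so no new data are needed.

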**CONFIDENTIAL**

204837

- Boxplot of Cmax/Dose at on-treatment MACE + thromboembolic event + hospitalization for CHF by subjects with or without on-treatment MACE + thromboembolic event + hospitalization for CHF
- Boxplot of Average TIW Dose at on-treatment MACE by subjects with or without on-treatment MACE
- Boxplot of Average TIW Dose at on-treatment MACE + thromboembolic event + hospitalization for CHF by subjects with or without on-treatment MACE + thromboembolic event + hospitalization for CHF
- Average TIW daprodustat dose will be summarized using mean, standard deviation, minimum, P25, median, P75, and maximum by participants with and without MACE.
- Average TIW daprodustat dose will be summarized using mean, standard deviation, minimum, P25, median, P75, and maximum by participants with and without MACE + thromboembolic event + hospitalization for CHF.

Average TIW daprodustat dose = average TIW daprodustat dose while on study treatment for participants without MACE/Combined MACE-related endpoint and before the event for participants with MACE/Combined MACE-related endpoint.

For the figures and summaries described above, the “On-Treatment” time window (“last non-zero dose date +28 days”, see Section 14.4.1) will be used to decide whether a subject should be considered with MACE/Combined MACE.

Daprodustat Safety Dose parameters (Dose at first MACE, Final Dose for Subjects without MACE, Dose at first MACE++, Final Dose for Subjects without MACE++) will be summarized using mean, standard deviation, minimum, P25, median, P75, and maximum by participants with and without MACE and MACE ++. Daprodustat Safety Special parameters (Cmax/ Dose at first MACE, Cmax/ Final Dose for subjects without MACE, Cmax/ Dose at first MACE++, Cmax/ Final Dose for subjects without MACE++) will be summarized using mean, standard deviation, minimum, median, maximum geometric mean, standard deviation of log-transformed data, and %CVb. A listing of the Safety Dose Parameters and a listing of the Safety Special Parameters will be provided.

### *Blood Pressure and Blood Pressure Medication Change*

Endpoint / Variables

 
• Observed and change from baseline in SBP, DBP, and MAP by visit
 
• Number of BP medications per participant by visit
 
• Change from baseline in the number or dose of BP medications per participant by visit
 
• N (%) of participants who had no change in the number or dose of BP medications from baseline by visit
 
• N (%) of participants who had an increase in the number or dose of BP medications from baseline by visit
 

- N (%) of participants who had a decrease in the number or dose of BP medications from baseline by visit

### Planned Exploratory Displays

- Observed and change from baseline in SBP, DBP, and MAP by visit are included in the summary of secondary safety analyses described in Section 8.1.
- The last on-treatment BP parameter change from baseline value (SBP, DBP, and MAP) recorded prior to the first change in BP medications will be summarized using mean, standard deviation, minimum, P25, median, P75, and maximum by treatment group. The first change in blood pressure medication occurs at the earliest time a new anti-hypertensive medication is administered or if the dose or frequency of an existing blood pressure medication is changed for any reason (increased, decreased, discontinued, or switched to another agent) in any anti-hypertensive medication, except medication records with frequencies of “Once only” and “PRN.”
- Number of BP medications per subject while the subject was on treatment will be summarized using mean, standard deviation, minimum, P25, median, P75, and maximum for each scheduled visit by treatment group. Number of BP medications for each subject at baseline is defined as the number of medications taken on the day before study treatment start date. For end of treatment, it is defined as the number of medications taken on last non-zero dose date + 1 day. The number of BP medications at all other nominal visits is defined as the number of medications taken on the day of the visit. Medication records with frequencies of “Once only” and “PRN” will be excluded from this summary.
- Change from baseline in the number of BP medications per subject while the subject was on treatment will be summarized using mean, standard deviation, minimum, P25, median, P75, and maximum for each scheduled visit by treatment group. The number of BP medications at baseline, end of treatment and all other nominal visits will be defined as described in the previous paragraph. Medication records with frequencies of “Once only” and “PRN” will be excluded from this summary.
- Additionally, the number and percentage of subjects who had no change, at least one change, an increase, a decrease, or a switch in the dosage or number of BP medications from baseline while the subject was on treatment will be summarized for each scheduled post-baseline visit by treatment group (see Section 14.6.4 for details of classifying BP medication changes). Medication records with frequencies of “Once only” and “PRN” will be excluded from this summary.
- Cumulative number of changes in on-treatment BP medications from baseline to Week 52 will be summarized by treatment group. For all records except with frequencies “Once only” and “PRN,” the cumulative number of changes will be summarized using mean, standard deviation, minimum, P25, median, P75, and maximum. The number and percentage of subjects with no change and at least one medication change will be displayed excluding “Once only” and “PRN” records. For subjects with at least one change, the number and percentage of subjects for each reason (increase, decrease, and switch) will be displayed (see Section 14.6.4 for details of counting BP medication cumulative changes) by treatment group. Number and percentage of subjects for each reason of BP medication change will be displayed by treatment group. Cumulative number of changes in on-treatment BP medication from baseline to Week 52 for “Once only” records only will be summarized using

mean, standard deviation, minimum, P25, median, P75, and maximum (see Section 14.6.4 for details of counting BP medication cumulative changes) by treatment group.

- Number and percentage of subjects with at least one PRN record at baseline and on-treatment BP medication during the period from study treatment start date to Week 52 will be displayed by treatment group.
- Number and percentage of subjects with any BP medication taken at baseline (the day before study treatment start date) and any on-treatment BP medication during the period from study treatment start date to Week 52 will be displayed by treatment group.

